15.1.2. Serious Adverse Event

An SAE is any untoward medical occurrence that at any dose:

- Results in death
- In the view of the Investigator, places the participant at immediate risk of death (a life-threatening event); however, this does not include an event that, had it occurred in a more severe form, might have caused death
- Requires inpatient hospitalization or prolongation of existing hospitalization
- Results in persistent or significant disability/incapacity

CONFIDENTIAL

The information contained herein may not be used, disclosed, or published without the written consent of Biogen MA Inc.

- Results in a congenital anomaly/birth defect
- Is a medically important event

A medically important event is an AE that, in the opinion of the Investigator, may jeopardize the participant or may require intervention to prevent one of the other outcomes listed in the definition above. (Examples of such medical events include allergic bronchospasm requiring intensive treatment in an emergency room or convulsions occurring at home that do not require an inpatient hospitalization.)

15.1.3. Prescheduled or Elective Procedures or Routinely Scheduled Treatments

A prescheduled or elective procedure or a routinely scheduled treatment will not be considered an SAE, even if the participant is hospitalized. The study site must document all of the following:

- The prescheduled or elective procedure or routinely scheduled treatment was scheduled (or was on a waiting list to be scheduled) prior to obtaining the participant's consent to participate in the study.
- The condition requiring the prescheduled or elective procedure or routinely scheduled treatment was present before and did not worsen or progress in the opinion of the Investigator between the participant's consent to participate in the study and the time of the procedure or treatment.
- The prescheduled or elective procedure or routinely scheduled treatment is the sole reason for the intervention or hospital admission.
 - If a participant is hospitalized due to local requirements for administration of the study treatment, the hospitalization should not be considered an SAE unless one of the requirements in Section 15.1.2 is met.

15.2. Safety Classifications

15.2.1. Investigator Assessment of Events

All events must be assessed to determine the following:

- If the event meets the criteria for an SAE as defined in Section 15.1.2.
- The relationship of the event to study treatment, [REDACTED] as defined in Section 15.2.2.
- The severity of the event as defined in Section 15.2.3.

CONFIDENTIAL

The information contained herein may not be used, disclosed, or published without the written consent of Biogen MA Inc.

15.2.2. Relationship of Events to Study Treatment, [REDACTED]

The following definitions should be considered when evaluating the relationship of AEs and SAEs to the study treatment.

Relationship of Event to Study Treatment	
Not related	An AE will be considered “not related” to the use of the investigational product if there is not a reasonable possibility that the event has been caused by the product under investigation. Factors pointing toward this assessment include but are not limited to the lack of reasonable temporal relationship between administration of the investigational product and the AE, the presence of a biologically implausible relationship between the product and the AE, or the presence of a more likely alternative explanation for the AE.
Related	An AE will be considered “related” to the use of the investigational product if there is a reasonable possibility that the event may have been caused by the product under investigation. Factors that point toward this assessment include but are not limited to a positive rechallenge, a reasonable temporal sequence between administration of the investigational product and the AE, a known response pattern of the suspected product, improvement following discontinuation or dose reduction, a biologically plausible relationship between the product and the AE, or a lack of an alternative explanation for the AE.
[REDACTED]	[REDACTED]
[REDACTED]	[REDACTED]
[REDACTED]	[REDACTED]
[REDACTED]	[REDACTED]
[REDACTED]	[REDACTED]

15.2.3. Severity of Events

The following definitions should be considered when evaluating the severity of AEs and SAEs:

Severity of Event	
Mild	Symptoms barely noticeable to participant or does not make participant uncomfortable; does not influence performance or functioning; prescription drug not ordinarily needed for relief of symptoms but may be given because of personality of participant.
Moderate	Symptoms of a sufficient severity to make participant uncomfortable; performance of daily activity is influenced; participant is able to continue in study; treatment for symptoms may be needed.
Severe	Symptoms cause severe discomfort; symptoms cause incapacitation or significant impact on participant’s daily life; severity may cause cessation of treatment with study treatment; treatment for symptoms may be given and/or participant hospitalized.

15.2.4. Expectedness of Events

Expectedness of all AEs will be determined by Biogen according to the Investigator’s Brochure.

15.3. Monitoring and Recording Events

15.3.1. Adverse Events

Any AE experienced by the participant between the time of first dose of study treatment and the participant’s final clinic visit (including the Follow-up Safety Visit) is to be recorded on the CRF, regardless of the severity of the event or its relationship to study treatment, [REDACTED]

[REDACTED] At each study visit, the Investigator will assess the participant for AEs and will record any new AEs or updates to previously reported AEs on the CRF.

AEs that are ongoing when the participant completes or discontinues the study will be followed by the Investigator until the event has resolved, stabilized, or returned to baseline status. AE outcome will be recorded on the CRF, as applicable.

CONFIDENTIAL

The information contained herein may not be used, disclosed, or published without the written consent of Biogen MA Inc.

15.3.2. Adverse Events of Special Interest

Immunogenicity is an AE of special interest that is under monitoring in all ongoing studies. Participants will also be monitored for possible infusion-associated AEs and/or hypersensitivity reactions during and after completion of the investigational medicinal product infusion.

15.3.3. Serious Adverse Events

Any SAE experienced by the participant between the time of the signing of the ICF and the participant's final clinic visit (including the Follow-up Safety Visit) is to be recorded on an SAE form, regardless of the severity of the event or its relationship to study treatment. SAEs must be reported to Biogen within 24 hours as described in Section 15.3.4. Follow-up information regarding an SAE also must be reported within 24 hours.

Participants will be followed for all SAEs until the final clinic visit (including the Follow-up Safety Visit). Thereafter, the event should be reported to Biogen only if the Investigator considers the SAE to be related to study treatment.

Any SAEs that is ongoing when the participant completes or discontinues the study will be followed by the Investigator until the event has resolved, stabilized, or returned to baseline status.

15.3.4. Immediate Reporting of Serious Adverse Events

In order to adhere to all applicable laws and regulations for reporting an SAE, the study site must formally notify Biogen within 24 hours of the study site staff becoming aware of the SAE. It is the Investigator's responsibility to ensure that the SAE reporting information and procedures are used and followed appropriately.

Reporting Information for SAEs

A report ***must be submitted*** to Biogen regardless of the following:

- Whether or not the participant has undergone study-related procedures
- Whether or not the participant has received study treatment
- The severity of the event
- The relationship of the event to study treatment [REDACTED]

To report initial or follow-up information on an SAE, fax a completed SAE form; see the Study Reference Guide's Official Study Contact List for complete contact information.

15.3.4.1. Deaths

Death is an outcome of an event. The event that resulted in death should be recorded on the appropriate CRF. All causes of death must be reported as SAEs within 24 hours of the study site becoming aware of the event. The Investigator should make every effort to obtain and send

CONFIDENTIAL

The information contained herein may not be used, disclosed, or published without the written consent of Biogen MA Inc.

death certificates and autopsy reports to Biogen. The term death should be reported as an SAE only if the cause of death is not known and cannot be determined.

15.3.5. Suspected Unexpected Serious Adverse Reactions

Suspected unexpected serious adverse reactions (SUSARs) are SAEs that are unexpected and judged by the Investigator or Biogen to be related to the study treatment administered.

Appropriate personnel at Biogen will unblind SUSARs for the purpose of regulatory reporting. Biogen will submit SUSARs (in blinded or unblinded fashion) to regulatory agencies according to local law. Biogen will submit SUSARs to Investigators in a blinded fashion.

15.4. Procedures for Handling Special Situations

15.4.1. Pregnancy

Participants should not become pregnant during the study and for 6 months (24 weeks) after their last dose of study treatment. If a female participant becomes pregnant, study treatment must be discontinued *immediately*. It is recommended that male participants should not father children during their participation in the study and for 6 months (24 weeks) after their last dose of study treatment.

The Investigator must report a pregnancy occurring in a female participant by faxing the appropriate form to Biogen within 24 hours of the study site staff becoming aware of the pregnancy. See the Study Reference Guide's Official Study Contact List for complete contact information. The Investigator or study site staff must report the outcome of the pregnancy to Biogen. A pregnancy is not considered an AE and should not be recorded on the AE CRF.

Congenital abnormalities and birth defects in the offspring of male or female participants should be reported as an SAE if conception occurred during the study Treatment Period.

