15.5. Contraception Requirements

All women of childbearing potential and all men must ensure that highly effective contraception is used during the study and for 6 months (24 weeks) after their last dose of study treatment. In addition, participants should not donate sperm or eggs for the duration of the study and for at least 5 times the half-life of BIIB092 or 6 months, whichever is longer, after their last dose of study treatment.

For the purposes of this study, women who do not meet one of the following criteria are considered to be physiologically capable of becoming pregnant and are, therefore, defined as women of childbearing potential:

- Postmenopausal:
 - 12 continuous months of natural (spontaneous) amenorrhea without an alternative medical cause and a serum FSH level >40 mIU/mL at Screening Visit 1.
 - 6 weeks after surgical bilateral oophorectomy with or without hysterectomy.
- Posthysterectomy.
- Female surgical sterilization (e.g., bilateral tubal ligation).

For the purposes of the study, highly effective contraception is defined as use of 2 of the following:

CONFIDENTIAL

The information contained herein may not be used, disclosed, or published without the written consent of Biogen MA Inc.

For female participants:

- Established use of oral, intravaginal, or transdermal combined (estrogen and progestogen containing) hormonal methods of contraception associated with the inhibition of ovulation.
- Established use of oral, injected, or implanted hormonal methods of contraception.
- Placement of an intrauterine device or intrauterine hormone-releasing system.
- Barrier methods of contraception with use of a spermicide, including condom, nonprescription sponge, or occlusive cap (diaphragm or cervical vault cap) used with spermicidal foam, gel, film, or cream suppository.
- Sex with a male who has undergone surgical sterilization (with the appropriate postvasectomy documentation of the absence of sperm in the ejaculate).

For male participants:

- Vasectomy with negative semen analysis at follow-up.
- Condoms with spermicide.
- Sex with a woman who uses the methods described for females if she is of childbearing potential.

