15.6. Safety Responsibilities

15.6.1. The Investigator

The Investigator's responsibilities include the following:

- Monitor and record all AEs, including SAEs, on the CRF regardless of the severity or relationship to study treatment, [REDACTED].
- Determine the seriousness, relationship to study treatment, [REDACTED], and severity of each event.

CONFIDENTIAL

The information contained herein may not be used, disclosed, or published without the written consent of Biogen MA Inc.

- Determine the onset and resolution dates of each event.
- Monitor and record all pregnancies in female participants and follow up on the outcome of all pregnancies.
- Complete an SAE form for each SAE and fax or email it to Biogen within 24 hours of the study site staff becoming aware of the event.
- Pursue SAE follow-up information actively and persistently. Follow-up information must be reported to Biogen within 24 hours of the study site staff becoming aware of new information.
- Ensure all AE and SAE reports are supported by documentation in the participants' medical records.
- Pursue AE follow-up information, if possible, until the event has resolved or become stable. Record AE follow-up information, including resolution, on the CRF, as applicable.
- Report SAEs to local ethics committees, as required by local law.

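### The birth-defect SAE rule in Protocol 15.4.1 ends with the Treatment Period, 24 weeks short of the protocol's own pregnancy-avoidance window, and leaves offspring of male participants without an explicit reporting route

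*Protocol*

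**What the plan says.** Protocol Section 15.4.1 contains two windows. For avoiding conception it says: "Participants should not become pregnant during the study and for 6 months (24 weeks) after their last dose of study treatment". For men, not fathering children over the same span is recommended. For harm to offspring it uses a shorter window: birth defects "in the offspring of male or female participants should be reported as an SAE if conception occurred during the study Treatment Period".

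Section 15.5 repeats the longer window, requiring that contraception "is used during the study and for 6 months (24 weeks) after their last dose of study treatment". Its limit on donating sperm or eggs may be longer still: "at least 5 times the half-life of BIIB092 or 6 months, whichever is longer, after their last dose of study".

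Four other provisions bear on the point:

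- Section 15.1.2 lists a congenital anomaly among the SAE criteria, with no condition on the date of conception.
- Section 15.3.3 covers SAEs that the participant experiences up to the final clinic visit, with a 24-hour reporting duty. After that visit: "Thereafter, the event should be reported to Biogen only if the Investigator considers the SAE to be related to study treatment".
- Section 15.4.1 requires a pregnancy in a female participant to be reported within 24 hours of the site becoming aware of it, and its outcome to be reported too. Neither duty carries a limit on conception date.
- Section 15.6.1 makes it an investigator duty to "Monitor and record all pregnancies in female participants and follow up on the outcome of all pregnancies".

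**The concern.** The protocol asks participants to avoid conception for 24 weeks after dosing ends, but its rule for classing harm to a child as an SAE stops when the Treatment Period stops. No reason is given for the difference. A site that follows the specific sentence in 15.4.1 would not class a birth defect as an SAE if conception fell in those 24 weeks.

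The classification matters. SAEs carry a 24-hour duty (15.3.3, 15.3.4), and suspected unexpected serious adverse reactions are by definition a subset of SAEs (15.3.5). A defect that is not classed as an SAE does not enter that pathway. The gap is widest for men. Section 15.4.1 names offspring of male participants, so they were meant to be covered, yet pregnancy reporting is confined to female participants.

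**Working it through.** The plan gives no figure to reproduce, so the check compares windows by week arithmetic and then traces the reporting routes.

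**Inputs.** From Protocol Sections 7.1 and 7.2 and Figure 1: last placebo-controlled dose at Week 76 and final visit at Week 90 without the LTE; LTE Treatment Period of 144 weeks from Week 80, last dose at Week 224, final visit at Week 238. From 15.4.1 and 15.5: avoidance for 24 weeks after the last dose.

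**Schedule check.** 76 + 14 = 90; 80 + 144 = 224; 224 + 14 = 238. All agree with the protocol.

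**Gap for a participant dosed to the end.**

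| | SAE rule ends | Avoidance window ends | Gap | Part after final visit |
|---|---|---|---|---|
| No LTE | Week 76 | 76 + 24 = Week 100 | 24 weeks | 100 − 90 = 10 weeks |
| LTE | Week 224 | 224 + 24 = Week 248 | 24 weeks | 248 − 238 = 10 weeks |

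Read literally, the 80 − 76 = 4 weeks between the two Treatment Periods are also uncovered for those who enter the LTE.

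**Share of calendar weeks from first dose.** 24/100 = 24% without the LTE and 24/248 = 9.7% with it, or (24 + 4)/248 = 11.3% if the four weeks are counted. These are shares of calendar time, not of exposure, conceptions or cases.

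**Early stopping.** If the Treatment Period is the scheduled 76 weeks and the last dose is at Week L, the uncovered part of the 24-week tail is max(0, L + 24 − 76). It is zero for L ≤ 52. Section 15.4.1 does not say whether it means the scheduled period or the participant's own dosing. On the second reading the tail is 24 weeks for everyone.

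**Routes for a birth defect when conception falls in the gap.**

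| Provision | Female participant | Male participant |
|---|---|---|
| 15.4.1 birth-defect sentence | Not met | Not met |
| 15.4.1 and 15.6.1 pregnancy and outcome | Applies; no deadline stated for the outcome | Does not apply |
| 15.1.2 SAE criterion | No conception limit, but 15.4.1 is the specific rule for offspring | Same |
| 15.3.3 | Refers to SAEs of the participant, so unclear for offspring; after the final visit, related events only | Same |

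A birth after a conception at Week 76 or later would ordinarily come after Week 90, and after a conception at Week 224 or later, after Week 238. So the relatedness limit in 15.3.3 would usually apply. The exception is a conception in Weeks 76 to 80 in someone who stays in the LTE: SAE collection is still open then, and the only doubt is whether 15.3.3 reaches offspring.

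**The case against.** The best case against the point is that little is lost. For women, the site must report every pregnancy it learns of, and the outcome, whenever conception occurred. A known birth defect therefore reaches the sponsor, at most without the SAE label. Section 15.4.1 says if, not only if, and 15.1.2 and 15.3.3 leave a general SAE route. Participants are aged 50 to 80. The primary endpoint is AEs and SAEs during the placebo-controlled period, and a child conceived after Week 76 would ordinarily be born after that period ends.

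Most of this stands, and it limits the point to classification and timing for women and to a missing explicit route for men. It does not remove the mismatch. The general route depends on reading 15.3.3 to cover offspring and, after the final visit, on the investigator's judgement of relatedness. Section 15.3.4, by contrast, requires SAE reports whatever the relationship.

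A reader might also infer that early stoppers have the largest relative gap. The documents do not support that. Under the scheduled 76-week Treatment Period, a participant who stops at Week 20 has a 24-week tail ending at Week 44, wholly inside the period.

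**Conclusion.** The point holds as an inconsistency in a safety-reporting rule, and it is minor. For a participant dosed to the end, the specific SAE rule is 24 weeks shorter than the avoidance window in the same section, plus four weeks between the periods if read literally. Women's pregnancies and outcomes stay reportable, without the SAE classification and its 24-hour duty. Offspring of male participants have no explicit route.

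This assumes that Treatment Period means the scheduled span and that sites follow the specific sentence in 15.4.1 ahead of the general definition in 15.1.2. Few cases are expected, and sample size, power and the primary endpoint are essentially unaffected.

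Two stronger readings should be resisted. A reader might infer that birth defects from later conceptions go unreported; for female participants the outcome-reporting duty contradicts that. A reader might also infer that the protocol assumes drug exposure throughout the 24 weeks. It sets avoidance and contraception requirements, gives no half-life, and for men only recommends not fathering children.

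**What to change.** In 15.4.1, replace the Treatment Period condition in the birth-defect sentence with the window already stated in 15.4.1 and 15.5: during the study and for 24 weeks after the last dose. Add that such events, when the site learns of them, are reported as SAEs within 24 hours, even after the final clinic visit and regardless of judged relatedness. Reconcile 15.1.2, 15.3.3 and 15.6.1 with this, and say expressly that it covers offspring of male participants. If the sponsor wants a different reporting window, it should state and justify it, and the same sections still need reconciling.

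The cost is a short wording change to the protocol and site safety instructions, with no added visit or procedure, and perhaps a few late reports after study exit. One limit remains: partner pregnancies are not collected and no visit falls in the last 10 weeks of the window, so detection still depends on the site hearing of the event.

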15.4.2. Overdose

An overdose is any dose of study treatment administered to a participant or taken by a participant that exceeds the dose assigned to the participant according to the protocol. Overdoses are not considered AEs and should not be recorded as an AE on the CRF; however, all overdoses must be recorded on an Overdose form and faxed to Biogen within 24 hours of the study site becoming aware of the overdose. An overdose must be reported to Biogen even if the overdose does not result in an AE. If an overdose results in an AE, the AE must be recorded. If an overdose results in an SAE, both the SAE and Overdose forms must be completed and faxed to Biogen. All study treatment related dosing information must be recorded on the dosing CRF.

15.4.3. Medical Emergency

In a medical emergency requiring immediate attention, study site staff will apply appropriate medical intervention, according to current standards of care. The Investigator (or designee)

CONFIDENTIAL

The information contained herein may not be used, disclosed, or published without the written consent of Biogen MA Inc.

should contact Biogen 24-hour emergency medical support: [name]. See the Study Reference Guide's Official Study Contact List for complete contact information.

15.4.3.1. Unblinding for Medical Emergency

In a medical emergency when knowledge of the participant's treatment assignment may influence the participant's clinical care, the Investigator or appropriate designee may access the participant's treatment assignment in the IRT system by accessing the internet or using a phone-based interface. Further information about the IRT unblinding function or 24-hour, 7-day-a-week support contact information is available in the IRT manual for the study.

The Investigator must document the reasons for unblinding in the participant's source documents. The Investigator is strongly advised not to divulge the participant's treatment assignment to any individual not directly involved in managing the medical emergency, or to personnel involved with the analysis and conduct of the study.

The Investigator can contact Biogen or its designee to discuss such situations, but such a discussion should not delay management of the medical emergency. The Investigator should inform Biogen or its designee as soon as possible if unblinding occurs.

